6.3.4 Pharmacokinetic Analysis

Pharmacokinetic sampling may be performed according to the study schedule and analysis may be performed at a later time.

6.3.5 Safety Analysis

All subjects entered into the study at Visit 1 will be included in the safety analysis. The frequencies of AEs by type, body system, severity and relationship to study drug will be summarized. SAEs (if any) will be described in detail. AE incidence will be summarized along with the corresponding exact binomial 95% two-sided confidence intervals.

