Electronic case report form (eCRF)	Sometimes referred to as clinical report form. A printed or electronic form for recording study participants' data during a clinical study, as required by the protocol.
Effectiveness	Effectiveness is the measure of the produced effect of an intervention when carried out in a clinical environment.
eGFR	Estimated glomerular filtration rate
End of the study	End of study (trial) is the date of the last visit or last scheduled procedure shown in the Study Schedule for the last active patient in the study.

Enrollment	The act of assigning a patient to a treatment. Patients who are enrolled in the trial are those who have been assigned to a treatment.
Enter	The act of obtaining informed consent for participation in a clinical trial from patients deemed eligible or potentially eligible to participate in the clinical trial. Patients entered into a trial are those who sign the informed consent form directly or through their legally acceptable representatives.
GCP	Good clinical practice
GEE	Generalized estimating equation
GMFM-88	Gross Motor Function Measure-88
HBV	Hepatitis B virus
HIV	Human immunodeficiency virus
ICF	Informed consent form
IFN	Interferon
IL	Interleukin
Institutional review board/ethical review board (IRB/ERB)	A board or committee (institutional, regional, or national) composed of medical and nonmedical members whose responsibility is to verify that the safety, welfare, and human rights of the patients participating in a clinical study are protected.
IP-10/CXCL10	Interferon inducible protein 10/ C-X-C motif chemokine 10
ISG	Interferon stimulating genes
IV	Intravenous
IVIg	Intravenous immune globulin
JAK	Janus kinase
Legal representative	An individual, judicial, or other body authorized under applicable law to consent on behalf of a prospective patient to the patient's participation in the clinical study.
MDBP	Myelin Disorders Biorepository Project
Patient	A study participant who has the disease or condition for which the investigational product is targeted.
PH	Pulmonary hypertension
PK	Pharmacokinetic
PPD	Purified protein derivative
QD	Once daily
QLS	Quasi-Least Squares
RA	Rheumatoid arthritis
SAE	Serious adverse event

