Screen	The act of determining if an individual meets minimum requirements to become part of a pool of potential candidates for participation in a clinical study. In this study, screening involves diagnostic procedures and/or tests (for example, x-rays, blood draws). For this type of screening, informed consent for these screening procedures and/or tests shall be obtained; this consent may be separate from obtaining consent for the study.
SLE	Systemic lupus erythematosus
STAT	Signal transducers and activators of transcription
STING	Stimulator of interferon genes
SUSAR	Suspected unexpected serious adverse reaction
ТВ	Tuberculosis
Treatment-emergent adverse event (TEAE)	Any untoward medical occurrence that either occurs or worsens at any time after treatment baseline and that does not necessarily have to have a causal relationship with this treatment.
ULN	Upper limit of normal
WBC	White blood cell

ABSTRACT

Context: (Background)

Aicardi Goutières Syndrome (AGS) is a multisystem, heritable disorder of innate immunity resulting in excessive interferon production. Interferon production causes injury to the brain, as well as the skin, liver, lungs, heart and many other organs. Treatment with Janus Kinase (JAK) inhibitors offers the promise of decreasing interferon signaling and limiting the morbidity of this devastating disorder.

Objectives: (Primary and important secondary objectives)

The primary objective is to assess safety as well as efficacy of baricitinib, a JAK inhibitor, in patients with Aicardi Goutières Syndrome. Efficacy will be determined primarily by changes in the AGS scale from baseline to 52 weeks of treatment. The secondary objectives include assessments of safety parameters, of therapeutic endpoints including an AGS symptom diary score; a surrogate biomarker, the interferon signaling gene score; and of functional neurologic measures (including GMFM-88 and longitudinal AGS scale measurements [in addition to and including baseline and 52 weeks]).

Study Design:

Open-label phase 2 clinical study.

Setting/Participants:

The setting: outpatient

The number of sites: single center

The number and description of participants including key eligibility criteria: eligible patients will have AGS with symptoms of neurologic disability, laboratory evidence of AGS related disease, or skin involvement, and no exclusion criteria making the administration of baricitinib less safe.

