4.3 Screening Visit

Screening (Visit 1) is applicable only to subjects not transferred from the JAGA Compassionate Use study (CHOP IRB Study #13205). The screening visit is a 2- to 28day period beginning at Visit 1. After receiving written informed consent from the patient's parent or a legal guardian (hereafter, "parent" refers to "parent or legal guardian"), patients will be assigned a patient number and will be considered entered into the study and study procedures may begin. Entry procedures will be performed per the Study Schedule (Appendices 1 and 2). During the screening period, patients must complete at least 14 days of diary entries before receiving the first dose of baricitinib (refer to the Patient Diary and Diary Score section below and Appendices 5 and 6). Current use of concomitant medications and reasons for use will also be collected on the eCRF, as well as start and stop dates. Particular note will be made of medications that are contraindicated (see Section 3.4.2) and which require dose adjustment (see Section 4.4).

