4.4 Study Treatment Phase

4.4.1 Enrollment

Consent

Written informed consent from the patient/patient's parent or a legal guardian will be obtained in person by the study investigators prior to any study procedure, with the exception of blood and urine tests, and daily diaries, which may be completed from the pre-screening period, after verbal consent.

For the patients transferred from the JAGA Compassionate Use study (CHOP IRB Study #13205), written informed consent from the patient/patient's parent or a legal guardian will be obtained by the study investigators prior to any study procedure completed as part of this investigator-initiated study.

Additionally, all the JAGA subjects (including the patients who do not consent and transition to the investigator-initiated JAK inhibitor treatment in AGS study will be asked to sign a consent form to allow for their data collected as part of the compassionate use program to be used for data analysis as part of the investigator-initiated study. The JAGA subjects who do not transition to the investigator-initated study will sign a separate consent form while the subjects who transition will be re-consented with a revised informed consent form including mention of this data transfer. Statistical considerations of this data transfer are detailed in Section 6.

Inclusion criteria

Entered patients are eligible for enrollment into the study (that is, eligible to receive baricitinib) only if they meet inclusion criteria (Section 3.4.1) at the time of Visit 2 and don't meet the exclusion criteria listed in Section 3.4.2.

Exclusion from Study Enrollment

Entered patients are ineligible for enrollment (that is, ineligible to receive baricitinib) and should be discontinued from the study if they meet any of the exclusion criteria listed in Section 3.4.2.

Patients who are entered, but do not meet enrollment criteria, should be discontinued from the study. These patients can be re-entered into the trial (that is, be reconsented) if the investigator believes that the patient might meet enrollment criteria at a future date, taking into consideration the volume of blood required for rescreening. Patients will receive treatment as clinically indicated for infections regardless of treatment decisions for baricitinib.

Rationale for Exclusion of Certain Study Candidates

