5 STUDY EVALUATIONS AND MEASUREMENTS

5.1 Screening and Monitoring Evaluations: Performed as Part of Clinical Care

5.1.1 Physical Examination

One complete physical examination (excluding pelvic and rectal examinations) will be performed at screening. This examination will determine whether the patient meets the criteria required to participate in the study and will also serve as a monitor for preexisting conditions and as a baseline for TEAE assessment. Body weight and height will also be recorded. Additional limited physical examinations will also be performed during the study (Study Schedule in Appendices 1 and 2). Fundoscopy may be completed as part of the physical exam if complaints of headache are present or irritability worsens on medication, and ophthalmology may be consulted as clinically indicated.

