8.5 IRB/IEC Notification of SAEs and Other Unanticipated Problems

The study coordinator is responsible for collecting and recording all clinical and laboratory data. Adverse events will be collected on subjects at all follow ups, as well as by phone or e-mail communication with parents 4 weeks following initiation of study agent. The reporting period for new AEs is the period from the start of study drug administration until one month after cessation. Follow-up reports on AEs should continue up to 30 days after the administration of drug if the AE did not resolve. For each AE, the site investigator will assess severity, and whether the event meets the definition of a serious adverse event and will report whether baricitinib treatment was interrupted or stopped, as well as the outcome of the AE. If the event is an SAE, both the site PI and the Medical Monitor will assess the relationship to drug.

If a non-serious adverse event is unresolved at the time of assessment, the site investigator will make a clinical assessment as to whether continued follow-up of the AE is warranted, and the results of this assessment must be documented. If a non-serious adverse event is unresolved at the time of discharge from the study, the Principal Investigator and the Medical Monitor will make a joint clinical assessment as to whether continued follow-up of the AE is warranted. Resolution is defined as the return to baseline status or stabilization of the condition with the expectation that it will remain chronic.

The PI will prepare aggregate reports of all adverse events (serious/not serious and expected, unexpected) for the DSMB and the IRB as required and for the FDA on an annual basis.

Lack of drug effect is not an AE in clinical studies, because the purpose of the clinical study is to establish drug effect.

Cases of pregnancy that occur during maternal or paternal exposures to investigational product or drug-delivery system should be reported. Data on fetal outcome and breast feeding are collected for regulatory reporting and drug-safety evaluation.

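### The safety set in 6.3.5 counts everyone who consented, but adverse events are collected only from first dose, so any never-dosed entrant lowers the reported AE incidence

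*Combined protocol and SAP*

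**What the plan says.** Section 6.3.5 names one population: "All subjects entered into the study at Visit 1 will be included in the safety analysis". It then promises AE incidence with exact two-sided 95% binomial intervals.

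The word entered has a defined meaning. The definitions table says "Patients entered into a trial are those who sign the informed consent form directly or through their legally acceptable representatives", and defines enrolment separately as assignment to treatment. Section 4.3 places entry at Visit 1: after written consent, "patients will be assigned a patient number and will be considered entered into the study and study procedures may begin".

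Section 4.4.1 provides for people who are entered but not treated. Those meeting an exclusion criterion are covered by "Entered patients are ineligible for enrollment (that is, ineligible to receive baricitinib) and should be discontinued from the study", and the section repeats that "Patients who are entered, but do not meet enrollment criteria, should be discontinued from the study".

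On collection of events, section 8.5 says "The reporting period for new AEs is the period from the start of study drug administration until one month after cessation". Section 8.3 defines an AE as something that happens to a subject who has had an intervention. The AE row in Appendix 2 is empty at screening and begins at Visit 2. The definition of a treatment-emergent event is consistent with this ("Any untoward medical occurrence that either occurs or worsens at any time after treatment baseline"), as is section 5.1.1, where the screening examination "will also serve as a monitor for preexisting conditions and as a baseline for TEAE assessment".

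**The concern.** The numerator and denominator come from different groups. Events can come only from people who took the drug, whereas the denominator includes everyone who signed consent. Each consented subject who is never dosed pulls every AE percentage down, together with its confidence limits (except a lower limit already at zero).

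Safety is a stated objective, and section 6.4 makes its analysis descriptive, so these percentages and intervals are themselves the safety result. Section 6.4 also expects that AEs may be rare. For an event seen in nobody, the upper confidence limit is the main information, and never-dosed subjects tighten it without adding any exposure.

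A second, smaller point concerns patients from the earlier compassionate use study (JAGA). Section 4.3 says Visit 1 does not apply to patients transferred from it. Read literally, 6.3.5 reaches consented subjects who took no drug but does not name treated transfers, whose data section 6.3.3.6 brings in for both efficacy and safety.

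**Working it through.** **Plan's own figure.** The plan gives no expected AE incidence and no safety-set size, so there is none to reproduce. Its only power figures, in section 6.4, reproduce (98.3% at effect size 0.77 and 80% at 0.53, with 30 pairs) and do not bear on this point.

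**Chain of reasoning.**
1. The safety set is everyone entered at Visit 1 (6.3.5).
2. Entered means consented, before eligibility is confirmed (definitions table, 4.3).
3. Some entered patients may never receive drug (4.4.1). Section 3.3 says the figure of about 55 allows for patients found ineligible during screening, and the drop-out text in 6.4 repeats the allowance.
4. New AEs are reported from first dose only (8.5, 8.3, Appendix 2).
5. A never-dosed entrant therefore contributes 1 to the denominator and 0 to the numerator.

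**Formulas.** Let D be the number dosed, k the never-dosed entrants, x the dosed subjects with the event, and n = D + k.
- Reported incidence = x/n. True incidence among the dosed = x/D.
- Relative understatement = 1 − D/n = k/n, whatever the value of x.
- Exact (Clopper-Pearson) limits: lower = 2.5th percentile of Beta(x, n − x + 1); upper = 97.5th percentile of Beta(x + 1, n − x).
- For x = 0, upper limit = 1 − 0.025^(1/n).

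**Inputs.** D = 45 is borrowed from the roughly 45 evaluable treated patients in section 6.4. The value x = 9 and the range of k are assumptions. The value k = 10 comes from the ceiling of 55: 55 − 45 = 10.

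| k | n | x/n | Exact 95% interval | Relative understatement | Upper limit if x = 0 |
|---|---|---|---|---|---|
| 0 | 45 | 9/45 = 20.0% | 9.6 to 34.6% | 0 | 7.9% |
| 1 | 46 | 9/46 = 19.6% | 9.4 to 33.9% | 1/46 = 2.2% | 7.7% |
| 2 | 47 | 9/47 = 19.1% | 9.1 to 33.3% | 2/47 = 4.3% | 7.5% |
| 5 | 50 | 9/50 = 18.0% | 8.6 to 31.4% | 5/50 = 10.0% | 7.1% |
| 10 | 55 | 9/55 = 16.4% | 7.8 to 28.8% | 10/55 = 18.2% | 6.5% |

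The last row is an extreme. It assigns the whole gap between 55 and 45 to never-dosed subjects, although section 6.4 also lists withdrawal, loss to follow-up and death as reasons for that gap.

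**The case against.** **There may be no never-dosed entrants.** The synopsis sets the same ceiling, 55, for entered and enrolled. Pre-screening (4.2) can remove unsuitable patients before Visit 1, and failed entrants may be re-entered (4.4.1). JAGA patients roll over without meeting the criteria (3.3.1), and some initially ineligible subjects are prospectively approved (3.3, 6.4). All of this stands, and it is why no definite size can be claimed. It does not repair the definition, which has to be right whether or not screen failures occur, and 3.3 and 6.4 expressly allow for them.

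**The illustration is constructed.** This also stands. The 45 is an evaluable count, so more than 45 could be dosed, and 9 events has no source. The relative understatement k/n does not depend on the choice of x.

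**Some events before dosing might be captured.** Section 8.1 monitors AEs throughout the study; 8.4 uses consent as the reference date for planned surgery; 8.5.1 mentions events related to a study procedure; 9.2.4 requires a case report form for every consented subject. None of these opens AE reporting before first dose. The first is general, the second only excludes certain surgeries, the third concerns events after the last dose, and the fourth concerns form completion.

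**6.3.5 says who is included, not what each percentage is divided by.** That is literally so, but an exact binomial interval needs an n, and the entered group is the only one named.

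**JAGA subjects are already covered.** Section 6.4 refers to all individuals, and 6.3.5 does not say only Visit 1 entrants count. This is fair: the JAGA wording is an unreconciled cross-reference, not a contradiction. However, the 6.4 wording does not restrict the set to dosed patients either, so it does not answer the main point.

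**Conclusion.** The concern holds, and it is minor. As written, 6.3.5 mixes a consent-based denominator with a dose-based numerator, and no section defines a dosed safety set. The resulting bias can only understate AE incidence, by the relative amount k/n.

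That fraction is unknown and may be zero. Under the assumed 45 dosed subjects it is 2.2% for one never-dosed entrant and 18.2% in the extreme case of ten. In absolute terms, a 20.0% incidence moves by 0.4 to 3.6 percentage points, against an interval about 25 points wide (34.6 − 9.6). The upper limit for an unseen event moves from 7.9% to 6.5% at most.

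The exact binomial method is sound. The study stopping rules in 8.7 count events and are unaffected. The JAGA wording cannot be sized because the number of transfers is not given.

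**What to change.** In section 6.3.5:
- Define the safety set as all subjects who received at least one dose of baricitinib, under JAGA or this protocol, and whose data may be used. Count AEs from first dose.
- List entered but never-dosed subjects separately, so they stay visible without entering the percentages.
- State whether events from the JAGA period count, consistent with 6.3.3.6 and 6.4.
- Cross-refer to the separate assessment of initially ineligible but approved subjects that 3.3 and 6.4 already require.
- Keep the exact binomial intervals.

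This takes two or three sentences with cross-references. It needs no new data for subjects treated under this protocol; the documents do not show how AEs were collected under JAGA, so that should be checked before the JAGA sentence is written. The only downside is that AE percentages may look slightly less favourable.

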3.2 Study Duration, Enrollment and Number of Sites

3.2.1 Duration of Study Participation

The study duration per subject will be up to 288 weeks, preceded by a screening period during which baseline testing will be obtained.

Study duration will be extended beyond Week 288 to long term follow up if transition to commercial supply is not possible for the patient.

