6.3.3.6 Special considerations

As described earlier, subjects enrolled in the Compassionate Use Treatment Protocol I4V-MC-JAGA (JAGA Compassionate Use study, CHOP IRB Study #13205) for whom commercial supply is not available, will be reconsented to the investigator-initiated JAK inhibitor treatment in AGS study. Data collected as part of their participation in IRB #13205 will be included as part of their longitudinal analysis, including baseline studies. Additionally, subjects who did not transition to this investigator-initiated study because they obtained commercial supply or discontinued participation in I4V-MC-JAGA will be consented via a separate consent form to permit inclusion of their data. For subjects who are considered lost to follow-up (unable to be reached after multiple attempts), a waiver of consent and HIPAA authorization will apply for inclusion of their data. This comprehensive approach is important to overall understanding of efficacy and safety in this ultra rare disease.

Because the JAGA Compassionate Use study protocol and this protocol are carefully aligned, we do not anticipate that any observed within patient changes in study outcomes will be due to differences in procedures between the two studies. However, we will perform sensitivity analyses, to determine if changes in outcomes with treatment differ between the two groups (data from patients enrolled only in the JAGA Compassionate Use study, data from patients who have been enrolled in both the JAGA study and the investigator-initiated JAK inhibitor in AGS study versus data from patients who are solely enrolled in the JAK inhibitor in AGS study). To the GEE model that includes time within patients, an indicator variable for JAK inhibitor in AGS study and a three way interaction term that is constructed as the product of time and treatment and the study indicator. If the three way interaction term is significant, this will indicate that the impact of treatment (change over time with treatment) differs significantly between groups.

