- s. Functional outcome assessments will be conducted at baseline and every six months.
- t. Three baseline IFN scores will be collected, each at least 5 days apart and not more than 60 days before start of study medication.
- u. Patients will be monitored for BK viremia at baseline, and every six months until they reach two years of age. Over two years of age, complete follow-up BK testing will be performed if any of the following is observed: blood in urine (as defined by 5-10 RBCS in HPF), protein in urine (positive), decrease in eGFR (30 <60 mL/min/1.73 m²). Follow- BK testing includes urine and serum BK testing. Abnormal urine results with urinary tract infection, in the absence of change in eGFR, do not necessitate BK testing.
- v. The creatinine should be measured using the IDMS (Isotopic Dilution Mass Spectrometry) technique to monitor the eGFR if available. Other methods are allowed but are not preferred. Laboratory testing using other methods will not be used to monitor the eGFR.
- w. These labs may be drawn (optional).
- x. For bone growth monitoring, IGF-1 will be completed yearly, and hand/wrist/fingers X-rays will be completed at baseline, 6 months, 12 months and then every 12 months (not after a bone age demonstrating complete growth).

* Visit schedule will be extended beyond Week 288 to long term follow up if transition to commercial supply is not possible for a patient. Visit will then be extended until patient transitions to commercial supply. The same tests and procedures that were completed during the study will be continued. Visit numbers will continue per the same numbering logic (232, 233, 234...).

Appendix 3. Dose Escalation Schedule for Patients with eGFR ≥60 mL/min/1.73 m2 or Normal eGFR for Age <24 Months (see footnote below^c)

If a change in the patient's weight during the study would place the patient in a different weight range, changes over time are permitted.

		Morning Dose	Noon Dose	Afternoon Dose	Evening Dose	Total Daily Dose	Dosing Frequency
FR ≥ 60 mL/min/1.73	m ²						
5-< 10 kg	Initial	1 mg	1 mg	0 mg	1 mg	3 mg	TID
	Escalation 1	1 mg	1 mg	1 mg	1 mg	4 mg	QID
10-< 20 kg	Initial	2 mg	2 mg	0 mg	2 mg	6 mg	TID
	Escalation 1	2 mg	2 mg	2 mg	2 mg	8 mg	QID
20-< 40 kg	Initial	3 mg	-	0 mg	3 mg	6 mg	BID
	Escalation 1	3 mg	—	2 mg	3 mg	8 mg	TID
≥ 40 kg	Initial	4 mg	_	-	4 mg	8 mg	BID
	Escalation 1	5 mg	—	_	5 mg	10 mg	BID
	Escalation 2	6 mg	_	_	6 mg	12 mg	BID

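### Section 6.3.5 reports AE incidence as crude percentages with no time horizon, although time at risk can run from weeks to beyond 288 weeks

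*Combined protocol and SAP*

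**What the plan says.** Section 6.3.5 is the whole AE analysis. It plans counts ("The frequencies of AEs by type, body system, severity and relationship to study drug will be summarized"), a detailed description of any SAEs, and one estimate with an interval: "AE incidence will be summarized along with the corresponding exact binomial 95% two-sided confidence intervals". The population is stated as "All subjects entered into the study at Visit 1 will be included in the safety analysis".

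Time at risk differs by subject:
- Section 3.2.1: "The study duration per subject will be up to 288 weeks", with extension for subjects who cannot move to commercial supply. The closing note of Appendix 2 leaves the end open: "Visit will then be extended until patient transitions to commercial supply".
- Section 8.5 collects new AEs from the first dose until a month after stopping, so the window lengthens with treatment.
- Section 6.4 foresees loss to follow-up and death before one year.
- Section 6.3.3.6 brings in compassionate-use data: "Data collected as part of their participation in IRB #13205 will be included as part of their longitudinal analysis, including baseline studies". It also admits data from JAGA subjects who never moved to this study, and gives understanding of safety as one of the reasons.

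No part of Section 6 plans a patient-time denominator, a time-to-event AE summary or a fixed AE window. Kaplan-Meier appears only in Section 6.3.1, for time to treatment.

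**The concern.** A crude proportion answers the question of how many subjects had the event while they happened to be observed. With one common observation period, that is a risk over a known time. Here there is no common period, so the figure has no stated horizon. Two groups, or two data cuts of the same group, can show different percentages at the same event rate.

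Safety is a stated objective and there is no concurrent control arm, so readers will rely heavily on these figures. Without exposure beside them, a reader cannot tell a higher event rate from longer observation.

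The denominator is also unclear. Under the protocol's definitions, "Patients entered into a trial are those who sign the informed consent form directly or through their legally acceptable representatives", so the safety set can include consented subjects who never took baricitinib and for whom no AE is collected. Section 4.3 says that Visit 1 does not apply to JAGA transfers, so read literally Section 6.3.5 leaves them out, whereas Section 6.4 says the safety analysis covers everyone.

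**Working it through.** **Plan's own figure.** There is none to reproduce. Section 6.3.5 gives no AE rate, precision target or exposure figure, and the power figures in Section 6.4 concern the AGS scale.

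**Inputs from the documents.** About 45 evaluable treated subjects (Section 6.4), up to about 55 enrolled (Section 3.2.2), and 288 weeks, which is 288/52 = 5.5 years (Section 3.2.1).

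**Assumptions.** A constant hazard of 5, 10 or 20 first events per 100 patient-years, and the follow-up mixes below.

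**Step 1: crude proportion against follow-up.** With hazard r per year and follow-up t years, P(at least one event) = 1 − exp(−r·t). At r = 0.05:
- t = 1: 1 − exp(−0.05) = 4.9%.
- t = 5.5: 1 − exp(−0.275) = 24.0%.
- 20 subjects at 1 year and 25 at 5.5 years: (20 × 4.9% + 25 × 24.0%)/45 = 15.5%.

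With exact weeks:

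| Rate per 100 patient-years | By week 52 | By week 288 | Ratio |
|---|---|---|---|
| 5 | 4.9% | 24.2% | 5.0 |
| 10 | 9.5% | 42.5% | 4.5 |
| 20 | 18.1% | 67.0% | 3.7 |

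**Step 2: the planned summary beside an exposure-adjusted one.** Take n = 45 and r = 0.10. Expected time at risk to first event is (1 − exp(−r·t))/r per subject, summed to T. For x subjects with an event (expected count, rounded), the rate is x/T. Its exact limits are χ²(0.025; 2x)/(2T) and χ²(0.975; 2x+2)/(2T).

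| Follow-up | Events | Crude % (exact 95% CI) | T, years | Per 100 patient-years (95% CI) |
|---|---|---|---|---|
| All 52 weeks | 4/45 | 8.9 (2.5–21.2) | 43 | 9.3 (2.5–23.9) |
| 15 each at 12, 104, 288 weeks | 9/45 | 20.0 (9.6–34.6) | 94 | 9.5 (4.4–18.1) |
| All 288 weeks | 19/45 | 42.2 (27.7–57.8) | 191 | 9.9 (6.0–15.5) |

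The first and last crude intervals do not overlap, although the event rate is the same. The rate stays near 10, as it must under a constant hazard.

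**Step 3: what the binomial interval covers.** In 100,000 simulated trials of the 12/104/288-week mix, at 5 to 20 per 100 patient-years, the interval covered the average risk of that mix 98.5% to 98.8% of the time. It covered the 52-week risk 21% to 57% of the time and the 288-week risk 0.1% to 43% of the time. So it is a sound, slightly conservative interval for a quantity tied to this particular mix.

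**Step 4: where a pooled rate fails.** Suppose 4 of 45 subjects have an event in year one, half a year in on average, and none occur later. At 52 weeks, T = 41 × 1 + 4 × 0.5 = 43 and the rate is 9.3. At 288 weeks, T = 41 × 5.54 + 2 = 229 and the rate is 1.7. A pooled rate therefore needs a fixed-time estimate beside it.

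**Step 5: denominator.** Nine subjects with an event give 9/45 = 20.0% (9.6–34.6). If ten untreated entrants are added, they give 9/55 = 16.4% (7.8–28.8).

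**The case against.** The strongest defence is that an exact binomial interval remains valid for independent subjects with unequal risks. That stands. A reader might infer that unequal follow-up breaks the interval, but step 3 shows it does not. The gap is the missing time horizon.

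Second, Section 6.4 calls the safety analysis descriptive and says comparisons may not be feasible, and Section 6.3.5 also plans counts and SAE descriptions. Section 6.3.1 says that primary and secondary assessments are first summarized by time of measurement, which may cover laboratory values. This limits the harm to interpretation, because no test is biased. It does not supply a horizon for AE incidence.

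Third, a rate per patient-year is independent of follow-up length only if the hazard is roughly constant. Section 4.6 describes neutropenia and leukopenia on treatment as typically transient, so this objection stands too. It is why the rate should join the crude percentage, not replace it.

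Two further inferences are tempting. One is that the fix would allow comparison with the adult data in Table 4. Those are themselves crude percentages over weeks 0–16, neither proposed summary matches them, and Section 6 plans no such comparison. The other is that DSMB reports will mislead. Their layout is not described, and meetings follow a charter that is not among the documents.

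Finally, very short exposure at the final analysis would come mainly from withdrawal, loss or death, since planned treatment runs to week 288. That is fair, but interim cuts and JAGA subjects who left early also vary.

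**Conclusion.** The point holds as a matter of interpretability. The planned AE percentage has no stated time horizon, so it rises with follow-up at a constant event rate and cannot be compared across subject groups or data cuts.

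Under a constant hazard of 5 to 20 per 100 patient-years, it is 3.7 to 5.0 times larger at 288 weeks than at 52 weeks. Those hazards and the follow-up mixes are assumptions. The documents give no AE rate per unit of time and no follow-up distribution, so the actual size is unknown. In particular, a reader might infer that the percentages will reflect length of follow-up as much as the drug, but the documents do not allow that to be quantified.

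The conflict over who is in the safety set needs no assumption, because it follows from Sections 4.3, 6.3.5 and 6.4 and the definitions. The change is worth making because it is cheap. The efficacy analysis is unaffected.

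**What to change.** In Section 6.3.5, keep the crude counts and percentages and add:

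1. The distribution of exposure: median, quartiles, range and total patient-years.
2. First events per 100 patient-years at risk, with each subject's time censored at the first event and exact Poisson 95% intervals, for SAEs, serious infections, thrombosis and grade 3–4 laboratory events.
3. Cumulative incidence at 52 weeks, by a fixed window or Kaplan-Meier, because the pooled rate alone assumes a roughly constant hazard.

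Define the safety set as all subjects with at least one baricitinib dose. State whether JAGA exposure and events count, and if so apply the same rule to numerator and denominator. Settle this first, since the rates depend on it.

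The cost is SAP wording and some programming. AE onset dates are already required (Section 8.3) and dispensing records are kept (Section 7.1.5). The protocol does not list first- and last-dose dates as case report fields, so confirm that they are held. The small downside is that JAGA dose and AE dates must be merged.
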